9.7 Other Analyses

9.7.1 Analyses of Pharmacokinetic Endpoints

All PK summaries outlined in this section will be created using the PK Analysis Set. Plasma PK concentration and PK parameters (except Tmax) summaries will additionally include the geometric mean and the geometric coefficient of variation (CV).

Descriptive statistics summaries of plasma concentrations will be provided by scheduled timepoint. Concentrations below the limit of quantification (BLQ) will be set to zero for summary statistics.

Mean plasma concentrations (+SD) will be plotted on a linear and semi-logarithmic scale versus nominal time points by treatment. Individual plasma concentrations will be plotted on a linear and semi-logarithmic scale versus actual sampling times. For each cohort, spaghetti plots of individual plasma concentrations on a linear and semi-logarithmic scale will also be presented. A reference line indicating the lower limit of quantification (LLOQ) will be included in plots, as appropriate.

Actual sampling times that are outside the sampling window ($\pm 10\%$ of nominal time) will be listed and used for PK parameters calculation but will be excluded from summary of concentration data.

All plasma concentration data will be listed by subject.

Urine PK concentration data will be listed and summarized.

The following PK parameters will be calculated for ARO-HSD PK concentration data for NHV and patients with suspected NASH, whenever data applicable:

Parameter	Definition
C_{\max}	Maximum observed plasma concentration
T_{\max}	Time to maximum observed plasma concentration (C_{\max})
AUC_{0-24}	The area under the plasma concentration versus time curve from the zero to 24 hours
AUC_{last}	The area under the plasma concentration versus time curve from the zero to the last quantifiable plasma concentration
AUC_{inf}	The area under the plasma concentration versus time curve from zero to infinity
$t_{1/2}$	Apparent terminal elimination half-life
CL/F	Apparent clearance (CL/F) calculated following extravascular drug administration

Vz/F	Apparent terminal-phase volume of distribution following extravascular drug administration
Ae _{0-24h}	Amount of unchanged drug recovered in urine over 0 - 24 hours post dose
fe _{0-24h}	Percentage of the administrated drug recovered in urine over 0 -24 hours postdose
CL _R	Renal clearance over a time interval calculated by Ae/AUC at the same time interval (0-24 h in this study).

Additional PK parameters such as dose/body weight normalized PK parameters may also be calculated as applicable.

The Sponsor will provide NCA analysis of plasma and urine PK data. Details about the PK parameter calculations are located in Appendix B.

The plasma and urine PK parameters will be listed and summarized descriptively by treatment. The diagnostic PK parameters listed in Appendix B will be listed only.

The Cmax and AUCs (AUClast and AUCinf) PK parameters from Cohort 1- 4 Day 1 will be compared across each dose level to assess dose proportionality. Statistical analyses will be done using a power model with the following general form:

$$\ln(\text{PK parameter}) = \alpha + \beta * \ln(\text{dose}) + \epsilon$$

where α is the y-intercept, β is the slope, and ϵ is the error. Estimates of α and β , and 90% confidence intervals (CIs) for β , will be provided for each PK parameter. Dose proportionality will be indicated if the Cmax and AUC 90% CIs for β all contain 1. The SAS code will be similar to the following:

```
proc reg data=adpp;
  by parameter;
  model ln(aval) = ln(dose) / clb alpha=0.1;
run;
```

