#### (Patient cohorts 1b, 3band 4b)

- Change in ALT and in AST as a marker of ARO-HSD activity compared to baseline
- Change in cytokeratin-18 compared to baseline
- Change in IL-1 $\beta$ , IL-6, IL-10, INF-gamma, and TNF- $\alpha$  compared to baseline
- Change in retinol and retinol binding protein compared to baseline
- Change in liver fat using MRI-PDFF compared to baseline
- Change in blood exosomal HSD17β13 mRNA levels (if feasible) compared to baseline
- Change in blood exosomal PNPLA3 mRNA levels (if feasible) compared to baseline
- Change in Enhanced Liver Fibrosis (ELF) Score at EOS compared to baseline
- Change in Pro-C3 at EOS compared to baseline
- Liver biopsy derived HSD17β13 mRNA expression compared to baseline
- Liver biopsy derived HSD17β13 protein expression compared to baseline in response to multiple doses of ARO-HSD (if scientifically feasible)
- Liver biopsy derived change in PNPLA3 mRNA expression compared to baseline
- Liver biopsy derived change in PNPLA3 protein expression compared to baseline in response to multiple doses of ARO-HSD (if scientifically feasible)

**Study Population/Patient Number:** This study will be conducted in adult males and females, aged 18 through 65 years (minimum of 19 years of age for NASH or suspected NASH patients) with BMI between 18.0 and 40.0 kg/m^2 enrolled and dosed as follows (see also Cohort Summary below):

NHV Cohorts 1, 2, 3, and 4: Each double-blind cohort will enroll eight (8) subjects (4 active: 4 PBO) with all cohorts planned to receive single escalating doses of ARO-HSD or placebo at dose levels of 25 mg (Cohort 1), 50 mg (Cohort 2),  $\leq$  100 mg (Cohort 3), and  $\leq$  200 mg (Cohort 4). These dose levels represent the highest dose that may be used in the cohort but after Cohort 1, the Data Safety Committee (DSC) may adjust the dose lower if indicated.

• Patient Cohorts 1b, 3band 4b: All patients will have suspected NASH and meet patient entry criteria. Cohorts are open label with up to 6 patients per cohort. All subjects will receive two doses of ARO-HSD at dose levels of 25 mg (Cohort 1b), ≤ 100 mg (Cohort 3b) and ≤ 200 mg (Cohort 4b). These dose levels represent the highest dose that may be used in the cohort but after Cohort 1, the DSC may adjust the dose lower if indicated.

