#### **Study Design/Methods:**

Participants who have signed an EC/IRB-approved informed consent form and have met all the protocol eligibility criteria during screening may be enrolled into the study in a double-blind or open label fashion depending on the cohort. Cohorts 1 through 4 (NHVs) will begin with administration of ARO-HSD or PBO to two sentinel participants (one ARO-HSD, one PBO). Following the Day 3 evaluation in these participants, if there are no significant safety concerns, the remaining participants in the cohort will be treated at the discretion of the Principal Investigator (PI). Dosing of participants will be staggered by at least 30 minutes such that no two participants will be dosed simultaneously. Sentinel dosing is not required in NASH/suspected NASH patient cohorts.

[figure not shown]
Dose levels by cohort are outlined in the Cohort Summary above and Dose Escalation Schedule below. NHV Cohorts 1 through 4 will enroll sequentially with patient cohorts opening for enrollment in a step-wise manner. Screening for all cohorts may begin once Cohort 1 has been opened for enrollment.

Dose escalation will require approval by the DSC based on all cumulative available safety data for prior cohorts, and through at least Day 15 of the current cohort as shown in Figure 1. Based on this cumulative safety data the DSC will vote to approve dose escalation to the next single dose NHV cohort as well as vote to open a NASH/suspected NASH patient cohort at the dose most recently tested in NHVs. Escalation to the next dose level will proceed until the highest planned dose level is completed, or the trial is halted prematurely by the PI, DSC, or Sponsor due to safety or other reasons. Where specified, dose levels represent the highest dose which may be used. The DSC may adjust doses downward if indicated based on review of available safety data and pharmacodynamic data (if available). All subjects who withdraw from the study prior to their End of Study (EOS) visit, for reasons other than an AE, may be replaced.

Cohort 1b (25 mg on Days 1 and 29) will enroll sequentially after Cohorts 3b and 4b are enrolled and will not require DSC approval to initiate enrollment as the dose is lower than the 200 mg top dose used in cohorts 4 and 4b which have already been opened by the DSC.

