# 5.8 Justification for Starting Dose in Humans

Reported pharmacokinetic properties for several oligonucleotide subclasses across species, including humans (Henry et al., 2001; Geary et al., 2003; Yu et al., 2001), indicate that the most appropriate method for extrapolating animal doses to human equivalent doses is the comparison of dose per unit body weight (mg/kg), rather than dose per surface area (mg/m²) or plasma exposure (AUC or Cmax). The human equivalent dose for oligonucleotide therapeutics can be extrapolated directly from monkeys to humans with a scaling factor of 1.0 on mg/kg dose administrations (Yu et al., 2015). Arrowhead has historically used 1:1 mg/kg scaling factor based on monkey NOAELs to determine starting dose in other siRNA first-in-human studies (ARO-HBV, ARO-ANG3, ARO-APOC3, and ARO-AAT first in human studies).

Extrapolated based on body weight, the proposed starting dose of 25 mg will be administered first to healthy volunteers in Cohort 1. The planned starting dose of 25 mg is approximately  $1/252^{nd}$  (assuming weight-based conversion and a 70kg subject) of the No-Observed-Adverse-Effect-Level (NOAEL) of 90 mg/kg based on the rat GLP study and  $1/840^{th}$  of the monkey NOAEL of 300 mg/kg. The highest planned dose in this study of 200 mg is  $1/31^{st}$  of the 90 mg/kg rat NOAEL and  $1/140^{th}$  of the monkey NOAEL. As ADS-006 is not cross reactive in rats or mice, but is fully cross reactive in cynomolgus and rhesus monkeys, monkeys are considered the pharmacologically relevant species. Regardless, there is a wide margin of safety between planned clinical doses and animal toxicology study NOAELs. The safety margins for each of the proposed ARO-HSD clinical doses (relative to rat or monkey NOAELs) is provided in Table 3 .

Table 3 Safety Margins of the Proposed ARO-HSD Clinical Doses (Assuming a 70 kg Subject)

ARO-HSD dose	Compared to rat NOAEL (90mg/kg)	Compared to monkey NOAEL (300mg/kg)
25 mg	1/252	1/840
50 mg	1/126	1/420
100 mg	1/63	1/210
200 mg	1/31.5	1/140

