#### 12.5 Pharmacokinetic Data

Plasma concentrations of ARO-HSD collected at specified time points post-dose from all participants at different dose levels will be used to calculate the following single dose pharmacokinetic parameters (Table 6):

Table 6 Definitions of Pharmacokinetic Parameters to be Assessed

te o Definitions of I had maconinette I at affected to be Assessed		
AUC 0-24	The area under the plasma concentration versus time curve from the zero to 24 hours	
AUC inf	The area under the plasma concentration versus time curve from zero to infinity	
C max	The maximum plasma concentration will be obtained directly from the plasma concentration time profile	
t max	The time to maximum plasma concentration will be obtained by inspection	
t 1/2	The half-life will be calculated by the equation $t_{1/2} = \ln(2)/k_{el}$	

The pharmacokinetic parameters will be determined using non-compartmental method(s). Descriptive statistics of pharmacokinetic parameters will include mean, standard deviation (SD), and coefficient of variation (CV), minimum and maximum. Dose-related trends in pharmacokinetic parameters will be assessed.

Pharmacokinetic parameters will be tabulated and summarized by dose level. The concentration-time profiles for each participant and the mean concentration-time profiles by dose level will be plotted with concentration presented on both linear and logarithmic scales.

Statistical analysis will be performed on the pharmacokinetic parameters using validated statistical software.

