2.2 Hypotheses and/or Estimations

No formal statistical hypotheses will be tested in this study. Any reported statistical tests will be considered exploratory.

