3. STUDY OVERVIEW

3.1 Study Design

The study will be conducted in approximately 50 adult males and females, aged 18 through 65 years (minimum of 19 years of age for NASH or suspected NASH patients) with BMI between 18.0 and 40.0 kg/m² enrolled and dosed as described in the table below. Cohorts 1, 2, 3, and 4 (NHVs) are double-blind, randomized with a 1:1 (active:PBO) ratio to reduce bias. Cohorts 1b, 3b and 4b are open-label with all subjects receiving active treatment and include patients with NASH or suspected NASH.

Cohort Summary

Cohort	Population	Blinding	# Subjects	Dosing Schedule
1	NHVs	Double blind	8 (4 active: 4 PBO)	25 mg Day 1 only
1b	Patients with suspected NASH (biopsies on screen and Day 71)	Open-Label	up to 6 (all active)	25 mg Days 1, 29
2	NHVs	Double blind	8 (4 active: 4 PBO)	50 mg Day 1 only
3	NHVs	Double blind	8 (4 active: 4 PBO)	\leq 100 mg Day 1 only
4	NHVs	Double blind	8 (4 active: 4 PBO)	\leq 200 mg Day 1 only
3b	Patients with suspected NASH (biopsies on screen and Day 71)	Open-Label	up to 6 (all active)	\leq 100 mg Days 1, 29
4b	Patients with suspected NASH (biopsies on screen and Day 71)	Open-Label	up to 6 (all active)	\leq 200 mg Days 1, 29

For NHV subjects in Cohorts 1 through 4, the duration of the study clinic visits is approximately 158 days from screening to the End-of-Study (EOS) visit. For subjects in Cohorts 1b, 3b and 4b, the duration of the study clinic visits is approximately up to 173 days from screening to the EOS visit.

The final analysis will be completed following database lock after the last subject's last visit. Individual cohorts may be summarized prior to database release; however, the final analysis will be based on all available data collected in the study.

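### SAP 9.7.1 treats a slope CI that contains 1 as showing dose proportionality, so noisier data earn that conclusion more easily whenever the true slope is not 1

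*SAP*

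**What the plan says.** SAP 9.7.1 describes the comparison this way: "The Cmax and AUCs (AUClast and AUCinf) PK parameters from Cohort 1- 4 Day 1 will be compared across each dose level". The model regresses the log of each parameter on log dose. Estimates of intercept and slope are reported, with a 90% CI for the slope. A decision sentence follows: "Dose proportionality will be indicated if the Cmax and AUC 90% CIs for" the slope all include 1. Neither this section nor the rest of the SAP gives an equivalence range, a maximum CI width or an inconclusive category. Nor does the SAP say what is concluded when a CI excludes 1.

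The protocol asks for less. Protocol 12.5 says "Dose-related trends in pharmacokinetic parameters will be assessed" and requires no verdict. SAP 2.2 adds that "Any reported statistical tests will be considered exploratory". Neither document gives a sample-size or precision calculation for this analysis (Protocol 12.1, SAP 3.2).

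**The concern.** A 90% CI that contains 1 shows only that a slope of 1 was not excluded. That can happen because the slope is close to 1 or because the data are too imprecise to tell. The SAP sentence treats both cases alike and attaches the favourable label to each. If the true slope is not 1, anything that widens the CI makes the label more likely: more between-subject variability, fewer usable values or a narrower dose range. If the slope is exactly 1, better precision brings no gain, because one CI contains 1 in 90% of trials whatever the variability.

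The plan allows information to be lost. Under SAP Appendix B, AUCinf is not calculated when the terminal fit is poor and may be excluded when the extrapolated area exceeds 20%. The synopsis lets the DSC lower doses after Cohort 1, which could shorten the range.

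PK is the only secondary endpoint (Protocol 6.2), and SAP section 1 makes the SAP the basis for the results in the study report. Protocol 5.6 looks to these cohorts for PK information for Phase 2 planning. A prespecified but unsupported statement of proportionality could therefore be carried forward.

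**Working it through.** The documents give no precision or power figure for this analysis, so there is nothing of the plan's own to reproduce.

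**Inputs from the documents**
- Four active subjects in each of Cohorts 1-4 (SAP 3.1): n = 16, residual df = 14.
- Doses of 25, 50, 100 and 200 mg. The two upper values are stated as maxima, but Protocol 5.8 refers to "The highest planned dose in this study of 200 mg" and the synopsis to the "200 mg top dose used in cohorts 4 and 4b which have already been opened by the DSC". The range is 8-fold.
- Two-sided 90% CI from ordinary regression; all three parameters must pass.

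**Assumptions, not in the documents**
- Between-subject CV of 20, 30, 40 or 50%.
- The same slope and CV for all three parameters.
- Correlation between parameters of 0 to 0.95. Values of 0.8 to 0.95 are taken as the more plausible, since the parameters come from the same concentration profiles.

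**Precision of one slope**
- Log doses lie at ±0.5 ln 2 and ±1.5 ln 2 from their mean, so Sxx = 4 × 5 × (ln 2)² = 9.609.
- Residual SD: σ = √ln(1 + CV²) = 0.198 / 0.294 / 0.385 / 0.472.
- Half-width: h = t(0.95, 14) × σ / √Sxx = 1.7613 × σ / 3.100 = 0.1125 / 0.1668 / 0.2189 / 0.2684.

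**What can still pass.** Take the residual SD equal to its assumed value.
- The largest observed slope that passes is 1 + h = 1.11 / 1.17 / 1.22 / 1.27.
- The dose-normalised exposure ratio over the range is 8^(slope − 1). At that boundary the point estimate is 8^h = 1.26 / 1.41 / 1.58 / 1.75.
- The upper confidence limit there is 8^(2h) = 1.60 / 2.00 / 2.49 / 3.05. The result would still count as proportional.

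**How often the label is earned.** For one parameter, P(CI contains 1) = P(|T| ≤ 1.7613), where T is noncentral t with 14 df and noncentrality (β − 1)√Sxx / σ. The joint rule was simulated with 200,000 trials per cell at correlations 0.8 and 0.95, and 100,000 at 0 and 0.5. Entries are percentages of trials.

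| True slope (ratio over 8-fold range) | Rule | CV 20% | CV 30% | CV 40% | CV 50% |
|---|---|---|---|---|---|
| 1.2 (1.52) | one CI | 9.2 | 35.8 | 54.5 | 65.2 |
| | joint, corr. 0 | 0.1 | 4.5 | 16.1 | 27.7 |
| | joint, corr. 0.5 | 1.2 | 13.1 | 28.4 | 40.0 |
| | joint, corr. 0.8 | 3.5 | 21.2 | 38.3 | 49.7 |
| | joint, corr. 0.95 | 6.1 | 28.4 | 46.4 | 57.7 |
| 1.3 (1.87) | one CI | 0.2 | 8.6 | 25.8 | 41.0 |
| | joint, corr. 0 | <0.1 | 0.1 | 1.7 | 6.8 |
| | joint, corr. 0.8 | <0.1 | 3.2 | 13.6 | 25.7 |
| | joint, corr. 0.95 | 0.1 | 5.7 | 19.6 | 33.3 |
| 1.5 (2.83) | joint, corr. 0.8 | <0.1 | <0.1 | 0.4 | 2.5 |
| | joint, corr. 0.95 | <0.1 | <0.1 | 0.8 | 4.6 |

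Slopes of 0.8 and 0.7 mirror 1.2 and 1.3, with ratios of 0.66 and 0.54. At slope exactly 1, the joint rule is met in 73, 76, 81 and 86% of trials at correlations 0, 0.5, 0.8 and 0.95, at every CV. So at correlations of 0.8 to 0.95 a truly proportional drug misses the label in 14-19% of trials, and better precision does not help.

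**The case against.** The strongest reply is that little depends on the sentence. The analysis is exploratory, and the slope and its CI appear beside the label. PK parameters are also summarised by treatment with geometric means and CVs, so a reader can judge proportionality directly. Neither the primary safety endpoint nor DSC escalation uses the rule. By the figures above, a slope of 1.5 is rarely missed, and the documents do not say that a 1.5-fold drift over an 8-fold dose range would matter for this drug. All of this stands, and it confines the effect to the stated PK conclusion.

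The size also depends on assumptions. With uncorrelated parameters the joint rule is met much less often (28% rather than 50-58% at slope 1.2 and CV 50%). The ratios of 1.6 to 3.05 are upper limits for a result exactly on the pass boundary, not typical results. The sentence also gives no label when a CI excludes 1, so the 14-19% at slope 1 are trials left without the favourable label, not trials declared non-proportional.

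These points change the illustrative size, not the logic. At every correlation examined, the pass rate rises with CV when the slope is not 1. An exploratory label does not make non-exclusion into evidence; it favours reporting estimates without a verdict.

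**Conclusion.** The rule is wrong as written. It draws a positive conclusion from failure to exclude a single value, and it rewards imprecision whenever the true slope is not 1. The direction needs no assumption about variability or correlation.

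The size does. With the planned 16 subjects and an 8-fold dose range, modest departures are often labelled proportional once CV reaches 30% or more. At correlations of 0.8 to 0.95, slope 1.2 passes in 21-28% of trials at CV 30% and 50-58% at CV 50%; slope 1.3 passes in 3-6% and 26-33%. Large departures are usually detected. The consequence is a possibly wrong statement about the only secondary endpoint in the study report. It should be corrected, but it does not threaten the primary analysis or the conduct of the trial.

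**What to change.** Keep the power model and the reported slope with its 90% CI. Replace the decision sentence in SAP 9.7.1 with text along these lines:

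> For each parameter we will report how many subjects contributed, the slope with its 90% CI, and the implied dose-normalised exposure ratio r^(slope − 1) with its 90% CI, where r is the highest dose given divided by the lowest. Interpretation will rest on the estimate and its precision. A CI that contains 1 will not by itself be taken as evidence of dose proportionality.

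If the sponsor wants a verdict, it should prespecify and justify its own margin for r^(slope − 1). For each parameter the result is then *proportional* (CI wholly inside the margin), *non-proportional* (wholly outside) or *inconclusive* (otherwise).

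The cost is one SAP sentence and a few added table entries. Model and data are unchanged, the ratio is a transformation of the slope and CI already planned, and Protocol 12.5 is still met. What is lost is a simple yes/no label.

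A margin would often give an inconclusive result at n = 16. At true slope 1 and CV 20/30/40/50%, one parameter's CI lies wholly inside 0.80-1.25 (slope 1 ± ln 1.25/ln 8 = 1 ± 0.107) in 8 / 0.2 / <0.1 / <0.1% of trials. It lies inside 0.5-2.0 (1 ± ln 2/ln 8 = 1 ± 0.333) in 99.9 / 91 / 63 / 35%. Both margins are illustrations, not proposals.

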9.7.2 Analyses of Pharmacodynamic Endpoints

Pharmacodynamic endpoints will be analyzed for cohorts 1b, 3b and 4b and will be created using the Safety Analysis Set.

For NASH biomarkers, descriptive statistics summaries will be provided for following biomarkers:

- ELF which consists of Hyaluronic acid (HA), Procollagen III amino terminal peptide (PIIINP), and Tissue inhibitor of metalloproteinase 1 (TIMP-1)]
- Cytokeratin-18
- PRO-C3
- IL-1 β , IL-6, IL-10
- INF-gamma, and TNF- α
- Liver Fibrosis Score
- Retinol binding protein

- Tumor Necrosis Factor
- Vitamin A

Derived changes and percent changes from baseline to each scheduled postdose visit will be included.

For hepatic imaging (MRI-PDFF and FibroScan), descriptive statistics summaries will be provided. Derived changes and percent changes from baseline to each scheduled postdose visit will be included.

Relative expression for HSD17B13 will be summarized and plotted using a dot plot. Relative expression is defined as $[2^{-(x_n - x_1)} - 1] * 100\%$

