## 5.6 Rationale for the Study

AROHSD1001 is a first in human dose-ranging study to assess the safety and tolerability of ARO-HSD in healthy volunteers and then in patients with NASH.

Treatment with ARO-HSD is expected to reduce hepatic production of the HSD17 $\beta$ 13 protein via RNAi. The magnitude of the reduction and duration of effect will depend on the dose. Since there has not been human clinical exposure to ARO-HSD, an effective therapeutic dose to administer to patients with NASH is unknown, although in the RNAi field, non-human primate potency and duration of activity are usually similar to that seen in humans.

The study begins with single dose administration to healthy volunteers to evaluate ARO-HSD for the purpose of understanding safety profile. There are no known serum biomarkers of HSD17B13, thus no pharmacodynamic data is expected from the NHV cohorts.

NASH/suspected NASH Patients will require administration of multiple doses of ARO-HSD to sustain hepatic silencing of HSD production. Accordingly, this study uses a multiple-ascending dose (MAD) design to determine the dose required to reach and sustain maximal knockdown in HSD17β13 levels, and the dose-response relationship in patients with suspected NASH (Cohorts 1b, 3b and 4b). These patients, having clinical characteristics consistent with NASH including elevated ALT and hepatic steatosis, would often require a liver biopsy to establish a definitive diagnosis of NASH. While biopsy may be part of the standard evaluations of these patients with suspected NASH, in this study, prudent limits make it a requirement only in NASH/suspected NASH Cohorts 1b, 3b and 4b. In the patient cohorts, dose response based on gene target mRNA and protein expression changes will be measured along with imaging and plasma markers of disease. It is critical to emphasize that as there is no known or established biomarker of HSD17B13 that liver biopsy is the only way to evaluate gene target silencing as a marker of pharmacodynamic effect. Thus, liver biopsy is critical to obtaining the data from this study needed to progress into Phase 2. The cohorts employing liver biopsy plan to enroll patients most likely to require liver biopsy as part of their standard clinical evaluation for NASH.

The addition for cohorts 1b and 3c in protocol version 5.0 aimed to assess gene target silencing at lower doses (Cohort 1b, ie, ARO-HSD 25 mg on Days 1 and 29) and allow evaluation of gene

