target silencing with less frequent dosing (Cohort 3c). However, Cohort 3c (ARO-HSD 100 mg on Days 1 and 85) is removed from protocol version 7.0 as the enrolled NHV cohorts as well as the three patient cohorts (3b, 4b and 1b) will provide sufficient preliminary data informing on safety, tolerability, pharmacodynamics, pharmacokinetics as well as dose response of multiple dose ARO-HSD necessary for future Phase 2 study planning.

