# 10.3.7 Liver Biopsy (only for Cohorts 1b, 3b and 4b)

With training and Sponsor approval, only those sites capable of processing biopsy tissue in accordance with the Laboratory and Biopsy Manuals will be required to obtain samples for protein expression analysis at the time points outlined in the Schedule of Assessments.

Samples will be used to assess effect of treatment on:

- HSD17B13 mRNA and PNPLA3 mRNA.
- Protein expression for HSD17B13 and PNPLA3 (if scientifically feasible).

The liver biopsy procedure and D1 dosing can be done on the same date. The only requirement is for the liver biopsy procedure to be completed before any other D1 procedures, especially dosing.

If the patient agrees to an additional biopsy core during Screening to confirm NASH diagnosis, the histopathology can be conducted as an option by the sites and histopathology costs will be covered by the Sponsor. This optional procedure should not be used to confirm patient eligibility.

Please see separate laboratory and biopsy manuals for specific instructions related to biopsy performance.

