9. STATISTICAL METHODS OF ANALYSIS

9.1 General Considerations

Descriptive statistics will be provided for selected demographic, safety and efficacy data. Descriptive statistics on continuous data will include the number of subjects, mean, median, standard deviation, minimum & maximum while categorical data will be summarized using frequency counts and percentages. Graphical summaries of the data may be also presented.

Unless otherwise noted, all summaries and figures will be presented by treatment, with NHV Cohorts 1-4 and Patient Cohorts 2b, 3b, and 4b presented separately. Subjects receiving placebo will be pooled across cohorts.

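### Dose response in liver HSD17B13 mRNA is a stated design purpose, but the SAP plans no interval and no between-dose estimate for it

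*SAP*

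**What the plan says.** **Purpose.** Protocol 5.6 gives the multiple-dose design two aims: to find the dose that reaches and sustains maximal HSD17B13 knockdown, "and the dose-response relationship in patients with suspected NASH (Cohorts 1b, 3b and 4b"). It adds that "dose response based on gene target mRNA and protein expression changes will be measured along with imaging and plasma markers of disease". The same section, explaining why Cohort 3c was dropped, lists among the information the remaining cohorts will supply the "dose response of multiple dose ARO-HSD necessary for future Phase 2 study planning". It also says that "liver biopsy is the only way to evaluate gene target silencing as a marker of pharmacodynamic effect".

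**Analysis.** SAP 9.7.2 states that "Relative expression for HSD17B13 will be summarized and plotted using a dot plot". Relative expression is defined there as [2^-(x_n - x_1) - 1] × 100%; x_n and x_1 are not defined. The statistics come from SAP 9.1: "Descriptive statistics on continuous data will include the number of subjects, mean, median, standard deviation, minimum & maximum", presented by treatment. Protocol 12.6 adds no model, contrast or interval for this endpoint.

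**Elsewhere in the SAP.** For PK, section 9.7.1 adds the geometric mean and geometric CV. It also fits a power model of the log parameter on log dose in Cohorts 1-4, with a 90% confidence interval for the slope. The distributional check in section 8.6 names secondary endpoints only, and biopsy mRNA is exploratory.

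**The concern.** Each patient has two liver biopsies, and the protocol regards biopsy as the only route to evidence of target silencing. The question put to those biopsies is how knockdown changes with dose. The SAP gives it no estimator: up to six values per dose would be tabulated and plotted, leaving a Phase 2 planner to judge by eye whether the doses differ.

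The scale is a second, smaller problem. Percent change is an exponential function of the measured difference and is bounded below at -100%. If x_n - x_1 is roughly symmetric, percent change is right-skewed, and its mean depends on the spread between patients as well as on dose. Two doses with the same median knockdown but different spread would then show different means, which could be misread as dose response.

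**Working it through.** **Inputs from the documents.** Three patient cohorts of up to 6, at 25, ≤100 and ≤200 mg (Protocol 7.1, Table 4); the relative-expression formula (SAP 9.7.2); the default statistics (SAP 9.1). The plan states no power or precision figure for this endpoint to reproduce. Its only number is the head count: 4 × 8 + 3 × 6 = 50, as stated.

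**Assumptions.** The documents give neither the SD of x_n - x_1 nor an expected knockdown. I take x_n - x_1 as normal with SD 0.5, 1.0 or 1.5 log2 units, and median knockdown k of 50%, 80% or 90%.

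**1. What the mean shows.** The median of 2^-(x_n - x_1) is 1 - k, and its mean is (1 - k) × exp[(SD × ln 2)²/2]. The multiplier is 1.062, 1.271 or 1.717 for the three SDs. At k = 80% and SD 1.0, mean knockdown = 1 - 0.20 × 1.271 = 74.6%.

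| Median knockdown | Mean, SD 0.5 | Mean, SD 1.0 | Mean, SD 1.5 |
|---|---|---|---|
| 50% | 46.9% | 36.4% | 14.2% |
| 80% | 78.8% | 74.6% | 65.7% |
| 90% | 89.4% | 87.3% | 82.8% |

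Two doses that both have 80% median knockdown, but SDs of 0.5 and 1.5, would differ by 78.8 - 65.7 = 13.1 points in the mean. In 100,000 simulated cohorts of six at SD 1.5, mean minus one SD fell below the impossible -100% in about 34% of cohorts (about 7% at SD 1.0 and none at SD 0.5).

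**2. What the planned median shows.** In the same simulations at k = 80%, the expected sample median knockdown was 79.7%, 78.6% or 76.7%. It is nearly unaffected.

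**3. The missing precision.** The 95% half-width for one cohort on the log2 scale is t(5 df) × SD/√6 = 2.571 × SD/2.449, or 1.05 at SD 1.0. Back-transformed around 80%, the limits are 1 - 0.20 × 2^1.05 = 58.6% and 1 - 0.20 × 2^-1.05 = 90.3%. At SD 0.5 the interval is 71% to 86%, and at SD 1.5 it is 40% to 93%.

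**4. What a between-dose estimate would offer.** For two doses with six patients each and an SD pooled over the three cohorts (15 df), the 95% half-width is 2.131 × SD × √(2/6). That is 0.62, 1.23 or 1.85 log2 units, a factor of 1.5, 2.3 or 3.6 in relative expression.

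For a slope on log2 dose at 25, 100 and 200 mg, the dose positions are 0, 2 and 3 doublings above 25 mg, with mean 5/3. So Sxx = 6 × (25/9 + 1/9 + 16/9) = 28. The 95% half-width per doubling is 2.120 × SD/√28 = 0.20, 0.40 or 0.60 log2 units. Over the 8-fold range (three doublings) it is 0.60, 1.20 or 1.80. These estimates can be made at the planned size, but they are imprecise if the SD is large.

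**The case against.** The case for leaving the plan alone has five parts.

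- **The summary is not only arithmetic.** The median, minimum and maximum are planned and individual values are plotted. With about six points per dose, a reader can see a patient who pulls the mean. This stands. A reader might infer that the reported knockdown will be biased, but the documents do not support that. A robust measure is already planned, the mean is a different quantity rather than a wrong one, and the larger gaps need an assumed SD of 1.0 to 1.5. At SD 0.5 and 80% knockdown the gap is 1.2 points.
- **mRNA is not the sole direct measure.** It is tempting to call it so, but Protocol 5.6 says this of biopsy, and Protocol 10.3.7 also lists "Protein expression for HSD17B13 and PNPLA3 (if scientifically feasible"). Of the two HSD17B13 biopsy measures, mRNA is the one not conditional on feasibility. Nor does Phase 2 planning rest on this endpoint alone: Protocol 5.6 also names safety, tolerability and PK.
- **The study is descriptive.** The objective is safety, the endpoint is exploratory, and there are no hypotheses and no sample-size calculation. This stands, and it makes the gap one of estimation, not error control. It does not remove the stated dose-response purpose. SAP 2.2 allows exploratory analysis, and SAP 9.7.1 already fits a dose model to healthy-volunteer cohorts with four active subjects per dose.
- **A single slope is a weak answer.** A straight line on log dose cannot locate a plateau, and a plateau is what the search for maximal knockdown implies. Cohorts 3b and 4b are specified as upper limits, so nominal doses may not be those given. This stands, so between-dose differences should come first.
- **Dose is not randomised.** The patient cohorts are open-label, and Protocol 7.1 has Cohort 1b enrolling after 3b and 4b. Any dose comparison is therefore confounded with enrolment period. This also stands and should be stated beside the results.

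**Conclusion.** The point holds as an inexpensive improvement to an exploratory analysis. A purpose that the protocol states plainly has no estimator in the SAP: no interval per dose and no difference between doses. This part rests on the text alone and needs no assumed SD.

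The scale problem is secondary and confined to the mean and SD. At 80% median knockdown the mean falls short by 1.2, 5.4 or 14.3 points for assumed log2 SDs of 0.5, 1.0 and 1.5, while the planned median moves by about 3 points at most. The skew follows from the formula if x_n - x_1 is roughly symmetric; the documents do not report it. Precision is poor enough to need showing: about 59% to 90% around 80% with six patients and an assumed SD of 1 log2.

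**What to change.** In SAP 9.7.2:

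1. Define x_n and x_1, and summarise x_n - x_1 on the log2 scale.
2. For each dose actually given, report the geometric-mean percent change with a 95% t-interval back-transformed from the log2 scale. Keep the planned median and dot plot.
3. Add exploratory between-dose differences on the log2 scale with 95% confidence intervals, also shown as ratios of relative expression.
4. Optionally, add a slope on log actual dose with its 95% interval, labelled descriptive.
5. State beside these results that the cohorts are open-label, not randomised between doses and enrolled sequentially, and that a slope cannot locate a plateau.

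At the same time, reconcile the patient cohorts named in SAP 9.1 (2b, 3b and 4b) with those in SAP 9.7.2 (1b, 3b and 4b), since 1b is the low end of any dose comparison.

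The cost is a few lines of SAP text and programming. No new data, visits or patients are needed.
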